Diabetes counseling, SMBG, hypoglycemia training/education		x	X																	Includes diabetes counseling, SMBG, hypoglycemia (see Sections 5.3, 8.3.3). After V3, review as needed
Participant Diary (Electro	onic) a	nd BC	G Met	er																
Dispense e-diary, glucometer, complete training		X																		
Dispense ancillary supplies as needed		X	Х	Х	Х		Х				Х		Х				Х		X	

			]	For p	roced	lures	at the	Scre	ening	/Lead	l In P	eriod l	[ (V1-V	/2) and	d Tre	atmen	t Perio	d II (V.	3-V22)	)
			it Visi	it 23 t	to Vis	it 37,	ЕТ, Ι									Period	l, plea	se see S	ection	1.3.2 Comments
Study Period I – Screenir	1g/Lea	d-In		•	•		•		Study	/ Peri	od II	- Trea	tment	Period	1					comments
Visit Number	1	2	3	4	5	6	7	8	9	10	11	12 13 14	15	16	17	18 19	20	21	22	
Weeks from Randomization	-3	-2	0	1	2	3	4	5	6	7	8	9 10 11	12	14	16	18 20	22	24	26	
Visit Interval Tolerance (days)		±3		±3	±3	±3	±3	±3	±3	±3	±3	±3	±3	±3	±3	±3	±3	±3	+3	
Fasting or Telehealth Visit			F			Т	F	Т	a	Т		Т	F	Т		Т		Т	F	T = telehealth visit; F = fasting visit; a see notes below
Diary compliance check			X	X	X	X	X	X	X	X	X	Х	Х	Х	X	Х	Х	Х	Х	Review FBG, hypoglycemia events, insulin dose
Patient-Reported Outcom	es (Pa	per)																		
Treatment-Related Impact Measure - Diabetes (TRIM-D)			Х																Х	
Patient-Reported Outcom	nes (Ele	ectron	ic)																	
Diabetes Treatment Satisfaction Questionnaire – Status (DTSQs)			X																	
Diabetes Treatment Satisfaction Questionnaire-Change (DTSQc)																			Х	
EQ-5D-5L			Х																Х	
Simplicity Questionnaire (SIM-Q) – Daily Basal Insulin			Х																	

			]	For p	roced	ures	at the	Scre	ening	/Lead	In P	eriod l	[ (V1-V	/2) and	l Tre	atment	t Perio	d II (V	3-V22)	
For	proced	ures a	t Visi	it 23 t	to Vis	it 37,	ET, I	U V, 8	01 an	d 802	(Stuc	ly Peri	iod III	) Safet	y F/u	Period	l, plea	se see S	ection	
Study Period I – Screenin	ng/Lea	d-In							Study	Peri	od II	- Trea	tment	Period	l					Comments
Visit Number	1	2	3	4	5	6	7	8	9	10	11	12 13 14	15	16	17	18 19	20	21	22	
Weeks from Randomization	-3	-2	0	1	2	3	4	5	6	7	8	9 10 11	12	14	16	18 20	22	24	26	
Visit Interval Tolerance (days)		±3		±3	±3	±3	±3	±3	±3	±3	±3	±3	±3	±3	±3	±3	±3	±3	+3	
Fasting or Telehealth Visit			F			Т	F	Т	a	Т		Т	F	Т		Т		Т	F	T = telehealth visit; F = fasting visit; a see notes below
Simplicity Questionnaire (SIM-Q) study intervention																			Х	
Basal Insulin Experience: Preference																			Х	

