Patient-Reported Outcomes	(Elect	ronic)		-	-	-						-		-		-	
Diabetes Treatment Satisfaction Questionnaire - Change						Х						Х					
EQ-5D-5L						Х						Х	Х				
Simplicity Questionnaire – Study Drug (SIM-Q)													Х				Administered only if ET occurs before Visit 26
Basal Insulin Experience: Preference												Х	Х				
Basal Insulin Experience: Likelihood of Incorporating into Routine												Х	Х				
Laboratory Tests and Samp	le Coll	ection	s														
Hematology						Х						Х	Х			Х	
Hemoglobin A1c (HbA1c)		Х				Х		Х				Х	Х			Х	

	For n	roced						`				•		d (801-8), please		ion 1.3.	1
								 						, preude s	Stu Perio	udy od III ty F/u	Comments
Visit Number	23 24	25	26 27	28	29	30	31	32	33 34	35	36	37	ET	UV	801	802	
Weeks from Randomization	28 32	36	40 44	48	50	52	60	64	68 72	74	76	78			80	83	
Visit Interval Tolerance (days)	±7	±7	±7	±3	±7	±3	±7	±7	±7	±3	±7	±3			+7	±7	
Fasting or Telehealth Visit	Т	F	Т	a	Т	F	Т	F	Т	a	Т	F	F		Т	F	T = telehealth visit; F = fasting visit; a see below notes
Clinical chemistry						Х						Х	Х			Х	
Glucose		Х						Х									
Lipid panel						Х						Х	Х			Х	
Urinalysis												Х	Х			Х	
Urine pregnancy													Х			Х	Additional pregnancy testing may be performed as necessary or if required by local regulations
C-Peptide												Х	Х				
eGFR (CKD-EPI)						Х						Х	Х			Х	
UACR						Х						Х	Х			Х	
Pharmacokinetic (PK) samples						Х						Х	Х			Х	All randomized participants

			F	for Tr	eatm	ent Po	eriod (	(V23-V	/37), I	ET, UV	, and	Safety I	F/u Perio	d (801-8	02)		
	For p	roced	ures at	Scree	ning	Perio	d I (V	1-V2)	and T	reatm	ent Pe	riod II (	V3-V22 )	, please	see Sect	ion 1.3.	1
					Stu	ıdy Po	eriod	II - Tr	-	nt Per	iod				Perio	ıdy od III ty F/u	Comments
Visit Number	23 24	25	26 27	28	29	30	31	32	33 34	35	36	37	ET	UV	801	802	
Weeks from Randomization	28 32	36	40 44	48	50	52	60	64	68 72	74	76	78			80	83	
Visit Interval Tolerance (days)	±7	±7	±7	±3	±7	±3	±7	±7	±7	±3	±7	±3	_		+7	±7	
Fasting or Telehealth Visit	Т	F	Т	a	Т	F	Т	F	Т	a	Т	F	F		Т	F	T = telehealth visit; F = fasting visit; a see below notes
Immunogenicity (ADA) samples						Х						Х	Х			Х	All randomized participants.
Stored Samples																	
Exploratory biomarker samples												Х	Х				
Randomization and Dosing																	
Insulin dose assessment /adjustment/documentation	Х	Х	Х	Х	Х	Х	Х	Х	Х	Х	X	Х	Х	Х			See Section 6.5.

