1.1. Objectives, Endpoints, and Estimands

Objectives	Endpoints			
• To evaluate treatment impact between LY3209590 and insulin degludec based on patient- reported outcomes questionnaires	 Change from baseline in TRIM-D at Weeks 26, 52, and 78 DTSQ change (DTSQc) from baseline at Weeks 26, 52, and 78 			
Tertiary				
To investigate the treatment impact of LY3209590 compared with insulin degludec on other measures of efficacy, safety, and patient-reported outcomes	 Efficacy: Percentage of participants achieving HbA1c < 7% at Weeks 26, 52, and 78 Percentage of participants achieving HbA1c < 7% at Week 26 without nocturnal hypoglycemia during treatment phase up to Week 26 Percentage of participants achieving HbA1c ≤ 6.5% at Weeks 26, 52, and 78 Change from baseline in fasting serum glucose at Weeks 26, 52, and 78 Safety: Incidence and rate of Level 2 hypoglycemia events during treatment period Incidence and rate of Level 3 hypoglycemia events during treatment period Incidence of positive treatment-emergent antibody of LY3209590 PK/PD: LY3209590 PK and concentration-response relationships to key safety and efficacy measures Potential intrinsic and extrinsic factors Patient-Reported Outcomes: Change from baseline in SIM-Q at Week 26 Frequency of responses to "Basal Insulin Experience: Likelihood of incorporating into routine" at Weeks 26 and 78 Frequency of responses to "Basal Insulin Experience: Preference" at Weeks 26 and 78 Change from baseline in EQ-5D-5L at Weeks 26, 52 and 			
	• Change from baseline in EQ-5D-5L at weeks 26, 52 and 78			

Abbreviations: CGM = continuous glucose monitoring; DTSQc = Diabetes Treatment Satisfaction Questionnaire – Change Version; HbA1c = hemoglobin A1c; SIM-Q = Simplicity Questionnaire; SMBG = self-monitoring of blood glucose; T2D = type 2 diabetes; TRIM-D = Treatment-Related Impact Measure – Diabetes.

Primary Estimand (for primary objective)

US registration

The *primary* clinical question of interest is: What is the treatment difference between LY3209590 and insulin degludec in change from baseline to Week 26 (Visit 22) in HbA1c in study eligible participants with type 2 diabetes (T2D) currently on basal insulin regardless of treatment discontinuation for any reason and regardless of initiation of rescue medication?

The *treatment regimen estimand* will be used for the primary objective and the attributes are described in the following table.

Treatment Regimen Estimand Attribute	Description		

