Modified Intent-to-Treat	All randomized participants who took at least 1 dose of study treatment.			
(mITT) Population	Participants will be analyzed according to the treatment they were assigned.			
Efficacy Analysis Set 1 (EAS1)	The data will include:			
for treatment regimen estimand	• mITT Population excluding participants discontinuing the study			
on efficacy measures	treatment due to inadvertent enrollment, and,			
	• all measurements regardless of the use of study treatment or the			
	initiation of rescue medication.			
Efficacy Analysis Set 2 (EAS2)	The data will include:			
for efficacy estimand on	• mITT Population excluding participants discontinuing the study			
efficacy measures	treatment due to inadvertent enrollment, and,			
	• measurements up to the early discontinuation of study treatment or			
	the initiation of rescue medication,			
	The data cutoff for participants who had an intercurrent event is defined by			
	the earliest date from below dates for individual participants except for the analysis on study dose:			
	- the date of last study dose ± 10 days for LY3209590, or ± 1 day for			
	Degludec			
	- the start date of the first rescue medication			
	The data cutoff for analysis on study dose is defined by the earliest date from			
	below dates for individual participants:			
	- the date of last study dose			
	- the start date of the first rescue medication			
Safety Analysis Set (SS)	The data will include:			
	• mITT Population, and,			
	• all measurement regardless of the use of study treatment or the			
	initiation of rescue medication			

4. Statistical Analyses

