4.4.2.1.3. Analysis of Fasting Blood Glucose

The analysis of fasting blood glucose (FBG), measured by SMBG, will be analyzed (in both CN and SI units). If a subject does not indicate which BG measurement was fasting, the FBG value will be assigned programmatically by designating the FBG as the first measurement between 5am-10am. These programmatically derived FBG values will also be included in the analysis.

4.4.2.2. **Other Safety Endpoints**

The safety measures based on CGM data will be analyzed as described in Section 4.4.2.1.1. For other safety measures, the details are provided in Section 4.6.

4.4.2.3. **Patient Reported Outcome**

The analyses for patient-reported outcomes will be based on the EAS2 data.

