4.4.2.3.1. Treatment-Related Impact Measure – Diabetes (TRIM-D)

The TRIM-D is a self-administered instrument, which assesses the impact of diabetes treatment on participants' functioning and well-being across available diabetes treatments (Brod et al. 2009). The TRIM-D consists of 28 items each assessed on a 5-point scale, where higher scores indicate a better health state, with a recall period of "over the past 2 weeks." In addition to an overall score, the TRIM-D items assess 5 domains of impact:

- Treatment Burden (6 items: Question 1a, Question 2a to 2e),
- Daily Life (5 items: Question 3a to 3b, Question 5a to 5c),
- Diabetes Management (5 items: Question 4a to 4e),
- Compliance (4 items: Question 6a, b, c, e), and
- Psychological Health (8 items: Question 6d, Question 7a to 7g).

Items within each domain are summed to obtain a raw domain score, which is then transformed to a scale of 0 to 100 to obtain a transformed domain score. The transformed domain score can be calculated by:

 $\frac{(\text{sum of raw score - sum of lowest possible raw score)}}{(\text{sum of highest possible raw score - sum of lowest possible raw score)}} \times 100$

For an example, Diabetes Management = $([sum of raw score -5]/[25-5]) \times 100$. If answer for the 5 questions in Diabetes Management (Question 4a to 4e) are all 1, then the sum of raw score is 5 and the transformed domain score is 0. All items can also be summed and transformed to obtain a transformed total score in a similar way.

Summary statistics for the transformed scores of each domain and all domains will be provided by study treatment. The scores at scheduled visits and the change from baseline will be analyzed by the MMRM model similar to the other efficacy endpoints (see Section 4.4.2.1). The last

non-missing postbaseline observations will be analyzed by an ANCOVA model using the independent variables of treatment, strata (country, and the type of basal insulin at randomization, baseline HbA1c stratum), and baseline value of the dependent variable as independent variables.

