4.4.2.3.2. Diabetes Treatment Satisfaction Questionnaire (DTSQ)

Diabetes Treatment Satisfaction Questionnaire-Status (DTSQs)

The Diabetes Treatment Satisfaction Questionnaire-Status Version (DTSQs) (Bradley and Lewis 1990; Bradley 1994) is a diabetes-specific patient-reported outcome instrument that assesses the overall treatment satisfaction and perceived frequency of hyperglycemia and hypoglycemia. It is appropriate for use in both T1D and T2D. The DTSQs consists of 8 items that assess treatment satisfaction as well as concerns about hyperglycemia and hypoglycemia over the past few weeks, prior to the visit. Each item is rated on a 7-point Likert scale. Items 1 and 4-8 are rated from 0 (very dissatisfied) to 6 (very satisfied) and can be summed up to produce a treatment satisfaction score ranging from 0 to 36. Items 2 and 3 are scored individually, and evaluate the perceived frequency of hyperglycemia and hypoglycemia and are rated from 0 (none of the time) to 6 (most of the time).

The collection of DTSQs is planned prior to the initiation of study treatment. The total scores of Item 1 and 4-8 and the individual scores of Items 2 and 3 will be summarized. Wilcoxon rank-sum test will be used for treatment comparison.

Diabetes Treatment Satisfaction Questionnaire-Change (DTSQc)

The Diabetes Treatment Satisfaction Questionnaire-Change Version (DTSQc) (Bradley 1999) was designed to overcome potential ceiling effects in the status version. The DTSQc has the same 8 items as the status version but is reworded slightly to measure the change in treatment satisfaction rather than absolute treatment satisfaction. Each item is scored on a scale of -3 to +3. For all items except item 2 (perceived frequency of hyperglycemia) and item 3 (perceived frequency of hypoglycemia), the higher the score, the greater the improvement in treatment satisfaction and a score of 0 represents no change. For Items 2 and 3, the lower the score, the better the perception. The ratings for Items 1 and 4-8 are summed to obtain a total treatment satisfaction score ranging from -18 to 18. Items 2 and 3 are scored individually.

The collection of DTSQc is planned after the initiation of study treatment. The total scores of Item 1 and 4-8 and the individual scores of Items 2 and 3 will be summarized. Wilcoxon rank-sum test will be used for treatment comparison.

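### DTSQc is not collected at early termination and is compared on on-treatment data only, so almost everyone who stops before Week 26 is left out of the treatment-satisfaction comparison

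*Protocol*

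**What the plan says.** SAP 1.1 lists "DTSQ change (DTSQc) from baseline at Weeks 26, 52, and 78" among the other secondary endpoints, as does Protocol Section 3. DTSQ and TRIM-D are the only two questionnaires at that tier.

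**Collection.** The schedule in Protocol 1.3.1 has the status version at Visit 3 and the change version first at Visit 22 (Week 26). In Protocol 1.3.2 the row "Diabetes Treatment Satisfaction Questionnaire - Change" is marked under Visit 30 (Week 52) and Visit 37 (Week 78), and its ET cell is empty. TRIM-D, EQ-5D-5L, SIM-Q for the study drug and both Basal Insulin Experience items are marked at ET. The SIM-Q entry carries the comment "Administered only if ET occurs before Visit 26". On timing, SAP 4.4.2.3.2 adds only that "The collection of DTSQc is planned after the initiation of study treatment".

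**Analysis.** SAP 4.4.2.3 states: "The analyses for patient-reported outcomes will be based on the EAS2 data". Protocol 9.3.3.2 agrees. Under SAP Section 3, EAS2 keeps "measurements up to the early discontinuation of study treatment or" the start of rescue. The cut-off is 10 days after the last dose for LY3209590 and 1 day for degludec (SAP 4.3.2). DTSQc is summarised and compared by Wilcoxon rank-sum test. TRIM-D gets an MMRM, and in addition its last "non-missing postbaseline observations will be analyzed by an ANCOVA model" (SAP 4.4.2.3.1). EQ-5D-5L is handled in the same way (SAP 4.5.3.1).

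**The concern.** The trial is open-label and compares a weekly with a daily injection. Dissatisfaction with the assigned insulin can be a reason for stopping it, and Protocol 7.1 includes the participant's own decision among the grounds for discontinuation. Scores can therefore be missing because of the quantity being measured.

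Four tertiary questionnaires are collected from people who leave early, and a higher-ranked one is not. I found no stated reason. With nothing collected between Week 0 and Week 26, and no analysis outside EAS2, the planned result answers how satisfied continuing participants are. A reader could easily take it as the satisfaction of everyone assigned to each insulin.

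**Working it through.** **1. The empty ET cell is genuine.** In Protocol 1.3.2 the DTSQc row and the EQ-5D-5L row have the same 17 cells. EQ-5D-5L is marked at Visit 30, Visit 37 and ET; DTSQc is marked at Visit 30 and Visit 37. The blank is not a column shift.

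**2. What happens to someone who stops before Week 26.**
- *Stops and leaves the visit schedule.* Protocol 4.1.1 gives this person an ET visit. No DTSQc is taken there or earlier, so no score exists.
- *Stops but stays.* Protocol 4.1.1 and 7.1 allow this, and the schedule then calls for DTSQc at Week 26. The score exists, but EAS2 excludes it.
- *Exception.* Someone who stops just before Visit 22 and attends within 10 days of the last LY3209590 dose, or 1 day of the last degludec dose, is still counted.

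EAS2 also drops scores after rescue, even when study insulin continues.

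The SAP 4.1 table lists the last collection after Week 0 as a post-baseline observation for patient-reported outcomes generally. That does not help either group: the first has no collection, and the second has one that falls outside EAS2.

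**3. How many.** Inputs from Protocol 9.5: 939 randomised 2:1 (626 and 313, Protocol 1.1) and 15% dropout at Week 26.
- Completers: 626 × 0.85 = 532.1 and 313 × 0.85 = 266.05, total 798. This reproduces the plan's 532, 266 and 798. Back-check: 798 / 0.85 = 939.
- Non-completers: 626 − 532 = 94 and 313 − 266 = 47, total 141, or 15.0% of 939.
- At assumed rates of 5%, 10% and 20% the totals would be about 47, 94 and 188.

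The split between the two routes is not given.

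**4. Direction and possible size of bias.** Let p be the proportion stopping in an arm, and d the amount by which stoppers' mean score lies below completers' mean score. Then:

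observed-case difference − all-participant difference = pL × dL − pD × dD (L = LY3209590, D = degludec).

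The documents give neither d nor arm-specific p, so these values are assumptions on the −18 to +18 total score:

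| pL, pD | dL, dD | Bias (points) |
|---|---|---|
| 15%, 15% | equal | 0 |
| 17%, 11% | 3, 3 | 0.17×3 − 0.11×3 = +0.18 |
| 17%, 11% | 10, 10 | 0.17×10 − 0.11×10 = +0.60 |
| 13%, 19% | 3, 3 | 0.13×3 − 0.19×3 = −0.18 |
| 13%, 19% | 10, 10 | 0.13×10 − 0.19×10 = −0.60 |
| 15%, 15% | 9, 3 | 0.15×9 − 0.15×3 = +0.90 |

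The two unequal splits both keep overall stopping at 15%: (2×17 + 11)/3 = 15 and (2×13 + 19)/3 = 15. The formula concerns means and the planned test is rank-based, so the table shows direction and conditions, not the effect on the test.

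**The case against.** The strongest reply is that the on-treatment target is deliberate. Protocol and SAP both assign questionnaires to EAS2, and wanting stoppers included is a wish for a different estimand. That stands, and it is why the EAS2 comparison should be kept. It does not explain why one questionnaire alone is missing at ET, or why DTSQc has no supportive analysis beside it.

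It can also be said that the same objective is covered by TRIM-D, which has ET collection and a last-observation analysis, and that the preference and likelihood items are collected at ET too. This limits the damage but does not supply a satisfaction score.

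Several stronger readings are tempting, and the documents do not support them:
- *The missing ET mark is the whole cause.* ET visits apply only to people who also leave the schedule. For those who stay, the cause is the EAS2 rule.
- *The lost scores cannot be recovered.* Those who stay have a score that an all-collected-data analysis would use directly.
- *Stopping is often the participant's choice.* Protocol 7.1 lists it without a frequency, and Protocol 7.2 expects study discontinuation to be uncommon.
- *Satisfaction is a main claim of the trial.* DTSQ is one of two other-secondary questionnaire endpoints, without multiplicity control.
- *The 10-day and 1-day cut-offs distort ET scores for DTSQc.* No such scores are planned. The unequal windows matter here for the narrow exception and for how a remedy is written.

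**Conclusion.** The gap is real and worth closing, but limited. DTSQc is the only post-baseline questionnaire without an ET mark. Together with the EAS2 restriction, this removes almost all participants who stop before Week 26, up to about 141 of 939 on the plan's assumed 15% dropout. That count is a planning figure, not an observed one, and excludes participants lost to the comparison through rescue alone.

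The comparison describes continuers. Bias is zero if stopping rates and the stoppers' shortfall in satisfaction are the same in both arms; otherwise it can go either way. Its size cannot be derived from the documents. No primary or key secondary conclusion depends on it.

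**What to change.** 1. In Protocol 1.3.2, add a mark for DTSQc in the ET column. If ET visits are already complete, items 2 and 3 can still be done.
2. In SAP 4.4.2.3.2, keep the EAS2 Wilcoxon comparison and add a supportive comparison of each participant's last collected DTSQc score. It should use ET scores and scheduled scores obtained after stopping or rescue, with one inclusion rule for both arms in place of the unequal cut-offs. Label it as all collected data regardless of discontinuation or rescue. Admitting such scores into EAS2 itself would mix off-treatment and post-rescue ratings into an on-treatment result.
3. Report missing DTSQc by arm and reason, at each visit.

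The cost is one eight-item questionnaire at a visit where others are already completed, a schedule edit, and a few SAP sentences. The drawback is that last collected scores come from mixed time points, some after a change of treatment, so this analysis supports the Week 26, 52 and 78 comparisons and does not replace them.

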#### Notes:

- Visit 1 (Week -3) procedures may be conducted over more than 1 day if all activities are completed within 3 days.
- Visit Interval The visit intervals including the allowable visit window should be scheduled relative to randomization.
- Visit 3 (Week 0) should occur 11-17 days after Visit 2.
- A local urine pregnancy test must be performed at Visit 3 (Week 0) with the result available prior to randomization and first injection of study drug(s) for women of childbearing potential only. Additional pregnancy tests (beyond those required per

SoA) should be performed at any time during the trial if a menstrual period is missed, there is clinical suspicion of pregnancy, or as required by local law or regulation.

- Visit 3 (Week 0) ADA sample should be collected pre-dose administration for all randomly assigned participants.
- Visit 3 (Week 0) (randomization) LY3209590 or insulin degludec will be administered during the study visit by site personnel.
- Visit 3 (Week 0) PK sample should be collected at least 15 minutes post-dose. Dose amount and time should be recorded immediately after dose administration in the participant's e-diary.
- Visit 4 (Week 1) weekly dose of LY3209590 will be administered by the participant during the study visit under observation of site personnel. The insulin dose amount and time is recorded for all doses.
- PK sampling- after Visit 3 may be collected at any time during the visit
- aVisit 9 (Week 6), Visit 28 (Week 48), and Visit 35 (Week 74) are eligible to be conducted remotely (that is, by telehealth visit in combination with mobile healthcare), as directed by the sponsor and allowed by local laws and regulations.
- Fasting "Visits" participants should not eat or drink anything but water for a minimum of 8 hours before the visit. If a participant attends these visits in a non-fasting state, the sample should still be collected as non-fasting. This will not be considered a protocol deviation.
- CGM Visits CGM collection should allow an interval of approximately14 days during the lead-in period and approximately 28 days for subsequent sessions post randomization. During the study blinded CGM sessions, only the study CGM device may be worn. Participants who routinely use personal CGM/FGM at study entry may not wear a personal CGM/FGM during the study required blinded CGM sessions. Refer to Section 8.1.5.2.
- Telehealth visit may be telephone or other technology.
- Unscheduled visits may occur at any time during the study.
- Grey shaded columns denote Telehealth Visits.

